10.0 Data and Specimen Banking: Not applicable

10.1 Data analysis

Specific Aim 1: To demonstrate the efficacy of inpatient integrated palliative and transplant care for improving patient-reported outcomes: Analyses will begin with descriptive and graphical summaries of the endpoints and evaluation of whether a normality assumption is reasonable for the endpoint or whether transformation is necessary. All statistical tests will be two-sided with an alpha level of 0.05. For all secondary and exploratory outcomes, we will use the false discovery rate (FDR) control method to address the issue of multiple testing. We selected an FDR of 0.15, which denotes the acceptable percentage of results that potentially represent false positives.⁶² The primary endpoint of the study will be to compare patient QOL (FACT-BMT) scores at week-2 between the study groups controlling for baseline values and demographic and clinical factors (as necessary for any imbalances in baseline variables) using a linear regression model. We will also compare secondary endpoints including patients' symptoms (ESAS), fatigue (FACT-Fatigue), depression and anxiety symptoms (HADS and PHQ9), and coping (Brief Cope) at week-2 between the study groups using linear regression models controlling for baseline values and clinical factors (as necessary for any imbalances in baseline variables). In the event that the effect of the intervention differs by transplant type, conditioning intensity, or other patient characteristics, we will examine these variables as interaction terms in the linear regression analyses. Finally, we will compute the effect size and Reliability Change Index to assess practical and clinical significance in the degree of change in the primary and secondary outcomes.

We will also utilize linear mixed models of the longitudinal data, allowing us to account for dependency among means over time and to control for demographic and clinical factors (as necessary for any imbalances in baseline variables) when examining change between groups in outcomes of interest across multiple time points (i.e., baseline, 2 weeks, 3, 6, and 12 months post-HCT). We will estimate practical and clinical significance of these outcomes (Cohen's d and Reliability Change Index).

Specific Aim 2: To assess the impact of inpatient integrated palliative and transplant care on caregiver-reported QOL and psychological outcomes: We will similarly compare caregivers' QOL

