Although we observed a large effect size for our palliative care intervention on patient-reported QOL during hospitalization (primary endpoint, Cohen's d = 2.9), we chose to be conservative in estimating the sample size for this trial given the proposed testing of the effect of the intervention on caregivers and post-HCT outcomes, expected attrition over time, and the proposed tests of mediation and moderation. In our prior study, we observed a 6.9 point difference (SD = 20) in QOL at week-2 between intervention and control group. With a sample size of 360, we will have 87% power to detect at least 6.9 point difference in patient QOL at week-2 between groups with a two-sided 0.05 significance level and assuming 10% missing data at week-2. Importantly, we only had 2% and 6.9% missing data at week-2 and 3-months post-HCT in our prior study. With a sample size of 360, we will also have > 80% power to detect a treatment difference in secondary patient-reported outcomes at week-2 (symptom burden, depression, and anxiety) with a two-sided 0.05 significance level. Assuming a missing data rate of 15% at three and six months, we will have 80% power to detect a 4.3 point difference in patient-reported QOL at 3 and 6 months post-HCT between the two groups (based on the difference we detected in our previous study). In our prior trial, we enrolled 94 (56%) caregivers and we noted a 1.6-point difference (SD = 3.3) in caregiver HADS-depression scores between the two study groups at week-2. Assuming that we enroll caregivers

PROTOCOL TITLE: Multi-Site Randomized Trial of Inpatient Palliative Care for Patients with Hematologic Malignancies Undergoing Hematopoietic Stem Cell Transplantation

for 50% of the patients included in this study (n = 180), we will have 90% power to detect a 1.6-point difference in caregiver HADS-depression scores at week-2 between the two groups with a two-sided 0.05 significance level.

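### The stated 80% power for a 4.3-point QOL difference at 3 and 6 months does not follow from the inputs in Section 10.2, which give about 47% at the only FACT-BMT SD in the plan

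*Combined protocol and SAP*

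**What the plan says.** Section 10.2 (Sample Size Calculation & Power Analysis) makes three power statements that can be checked or partly checked.

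- **Patient QOL at week 2 (primary).** In the prior single-center trial, "we observed a 6.9 point difference (SD = 20) in QOL at week-2 between intervention and control group". With 360 patients, 10% missing and two-sided 0.05, "we will have 87% power to detect at least 6.9 point difference in patient QOL at week-2 between groups".
- **Caregiver HADS-depression at week 2.** In the prior trial, "we noted a 1.6-point difference (SD = 3.3) in caregiver HADS-depression scores between the two study groups at week-2". With 180 caregivers, "we will have 90% power to detect a 1.6-point difference in caregiver HADS-depression scores at week-2 between the two groups".
- **Patient QOL at 3 and 6 months.** "Assuming a missing data rate of 15% at three and six months", the plan states that "we will have 80% power to detect a 4.3 point difference in patient-reported QOL at 3 and 6 months post-HCT between the two groups". The 4.3 points are attributed to the prior trial. No SD is given for these visits.

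Section 10.1 (Data analysis) plans a baseline-adjusted linear regression at week 2. For the later visits it says: "We will also utilize linear mixed models of the longitudinal data, allowing us to account for dependency among means over time". Section 10.2 does not refer to the mixed model and gives no variance or correlation for it.

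Section 10.2 also describes the prior week-2 QOL effect as large, with Cohen's "d = 2.9), we chose to be conservative in estimating the sample size for this trial".

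**The concern.** The 3- and 6-month target (4.3 points) is much smaller than the week-2 target (6.9 points), and fewer patients are expected to contribute (85% rather than 90%). Yet the stated power falls only from 87% to 80%. On one common basis that cannot be right, and the text mentions no change of SD, model or adjustment between the two sentences. Nor does it say whether the 80% applies to each visit or to the two visits together.

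Aim 1 hypothesises a QOL benefit at 3, 6 and 12 months, and longitudinal FACT-BMT is the first secondary endpoint in Section 8.2. This sentence is the only power statement for patient QOL after the transplant hospitalization. If power is near 47%, a true 4.3-point effect would be missed slightly more often than found; if it is 80%, it would be missed one time in five. The reader cannot tell which was planned for.

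**Working it through.** **Inputs.** From Section 10.2: N = 360; 10% missing at week 2 and 15% at 3 and 6 months; week-2 QOL difference 6.9 with SD 20; caregiver difference 1.6 with SD 3.3 and n = 180; later QOL difference 4.3. From Sections 9.1 and 10.1: 1:1 allocation, two-sided 0.05.

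**Formula.** For n evaluable patients per arm, difference δ and standard deviation SD, power ≈ Φ(δ / (SD·√(2/n)) − 1.96). The exact figures use the noncentral t.

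**Step 1: reproduce the plan's own figures.**

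- Week-2 QOL: 360 × 0.90 = 324, so n = 162. SE = 20·√(2/162) = 2.222; 6.9/2.222 = 3.105; Φ(1.145) = 87.4% (noncentral t 87.2%). Stated: 87%.
- Caregivers: n = 90. SE = 3.3·√(2/90) = 0.492; 1.6/0.492 = 3.25; Φ(1.29) = 90.2% (noncentral t 89.9%). Stated: 90%. This one reproduces with no allowance for missing data.

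**Step 2: apply the same calculation at 3 and 6 months.** 360 × 0.85 = 306, so n = 153. SE = 20·√(2/153) = 2.287; 4.3/2.287 = 1.880; Φ(−0.080) = 46.8% (noncentral t **46.6%**). Stated: 80%.

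**Step 3: look for a simple variant that gives 80% at SD 20.**

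| Variant | Power |
|---|---|
| 10% missing (162 per arm) | 49% |
| No missing data (180 per arm) | 53% |
| One-sided 0.05, 15% missing | 59% |
| One-sided 0.05, no missing data | 65% |
| Two-sided 0.15, 15% missing | 67% |
| Two-sided 0.15, no missing data | 73% |

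None reaches 80%.

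**Step 4: back-solve.** At 153 per arm, 80% power needs a standardized difference of 0.3213.

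- For 4.3 points: SD = 4.3/0.3213 = 13.38.
- At SD 20: difference = 0.3213 × 20 = 6.43 points.
- At SD 20 with baseline adjustment, where the effective SD is 20·√(1 − r²): r = √(1 − (13.38/20)²) = 0.743.

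Allowing for rounding of the stated powers, 87% implies an effective SD of 19.9 to 20.2 and 80% implies 13.3 to 13.5. An effective SD of 13.38 at week 2 would give more than 99% power there, not 87%.

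**Step 5: what would support 80%.** Every SD other than 20 and every correlation below is an assumption; n = 153 per arm and δ = 4.3 throughout.

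| Basis | Power |
|---|---|
| Unadjusted, per visit: SD 18 / 16 / 15 / 14 | 54.9 / 64.9 / 70.5 / 76.4% |
| Baseline-adjusted, per visit, SD 20: r = 0.5 / 0.7 | 58.1 / 74.7% |
| Baseline-adjusted, per visit, SD 18: r = 0.7 | 83.1% |
| Baseline-adjusted, per visit, SD 16: r = 0.5 / 0.6 | 77.2 / 83.4% |
| Baseline-adjusted, per visit, SD 15: r = 0.4 / 0.5 | 77.8 / 82.3% |
| Baseline-adjusted average of both visits, SD 20, common correlation 0.5 / 0.6 / 0.7 | 75.5 / 80.7 / 87.8% |

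The last row uses effective SD = 20·√((1 + ρ)/2 − r²) with ρ = r, giving 14.14, 13.27 and 12.00.

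**Step 6: Cohen's d.** 6.9/20 = 0.345. The stated 2.9 is about 8.4 times larger (2.9/0.345). No power figure in the section depends on it.

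**The case against.** The SD of 20 belongs to week 2, which Section 9.7 says was timed to the peak of symptoms. Scores may be less variable at 3 and 6 months, and the 4.3 points come from a prior trial whose SD at those visits is not in the documents. The planned analysis for these visits is a mixed model, not an unadjusted t-test, and Step 5 shows that ordinary-looking combinations reach 80%. On this view the figure is under-specified rather than miscalculated, and printing 47% would replace one unsupported number with another.

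Much of that stands. The documents do not show that 80% is unattainable, and they cannot distinguish a plain slip from an unstated basis. Two matching week-2 figures also do not fix the method for a later visit, particularly as one allows for missing data and the other does not. A null long-term result could in any case be read from its confidence interval.

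It does not rescue the sentence. A power figure needs an SD, and the only one given for this scale produces 47%. Section 10.1 also plans baseline adjustment at week 2, yet the 87% is reproduced without any credit for it. If adjustment or repeated measures were credited only at the later visits, the plan has to say so.

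**Conclusion.** The concern holds. The 80% does not follow from what Section 10.2 states. On the basis that reproduces the section's other two figures, the power is 46.6%, a shortfall of about 33 percentage points, and the difference detectable with 80% power is about 6.4 points rather than 4.3. The 47% rests on two assumptions: that SD 20 carries over from week 2, and that each visit is compared without adjustment. With a smaller SD, a strong baseline correlation or averaging over visits, 80% may be correct, but the plan attaches none of these to the figure.

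The endpoint is secondary. The primary power is reproduced, and neither the sample size nor the analysis is in question. The point should be fixed, but it does not threaten the trial. The Cohen's d of 2.9 is a separate, smaller inconsistency.

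**What to change.** Keep N = 360 and amend the paragraph in one of two ways.

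1. If the 80% was derived on another basis, state the SD at 3 and 6 months, the correlations (with baseline and between visits), the model, and whether the target is per visit or averaged. Say that this differs from the unadjusted week-2 calculation.
2. If no such basis can be documented, restate the figure as about 47% power per visit for 4.3 points with 15% missing, with 80% reached at about 6.4 points, assuming SD 20 and no adjustment.

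Separately, change the Cohen's d of 2.9 to about 0.35, or state what the 2.9 measures.

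The cost is wording and figures in one paragraph, with no extra patients and no change to the analysis. Under the second option the long-term power shown is less favourable.

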9.0 Procedures Involved

9.1 Study design

We propose a multi-site randomized controlled trial of inpatient integrated palliative and transplant care versus transplant care alone in 360 patients with hematologic malignancies hospitalized for HCT and 180-360 of their caregivers. Patients will be randomized in 1:1 fashion and stratified by study site and transplant type (autologous vs. allogeneic). As autologous and allogeneic HCT have significantly different courses of recovery post-transplant,¹ we will stratify by the type of transplant to ensure adequate and balanced representation between the two study groups

9.2 Palliative Care Intervention:

Patients randomized to the palliative care intervention will meet with a palliative care clinician within 48 hours of randomization (excluding weekends). After the initial visit, the palliative care clinicians will meet with patients at least two times per week during their hospitalization. Patients, caregivers, or the palliative care clinician may initiate additional visits as needed.

Table 2: Palliative Care Intervention Domains		
Domain	Elements	Key Points
Therapeutic Relationship	
 • Introducing role palliative care • Understanding the patient and caregiver experience • Building trust with the patient and caregiver 	
 • Develop a strong therapeutic relationship with patients and caregivers • Learn about the values, life goals, and experiences of patients and their caregivers both prior to and after the cancer diagnosis • Develop trust and credibility with patients and caregivers by providing reassurance and outlining parameters of communication

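### The 90% caregiver power in Section 10.2 leaves no room for missing week-2 data; with the allowance used for patients it would be about 87%

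*Combined protocol and SAP*

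**What the plan says.** The caregiver power statement closes Section 10.2. It takes its effect from the prior single-center trial, where "we noted a 1.6-point difference (SD = 3.3) in caregiver HADS-depression scores between the two study groups at week-2". It then supposes that caregivers enrol "for 50% of the patients included in this study (n = 180), we will have 90% power to detect a 1.6-point difference", tested "with a two-sided 0.05 significance level". The 180 is therefore a count of caregivers enrolled, half of the 360 patients. The caregiver statement mentions no missing data.

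Earlier in the same paragraph, the patient power for FACT-BMT at week 2 is given as 87% with 360 patients, "assuming 10% missing data at week-2". For patient QOL at 3 and 6 months the paragraph assumes 15% missing.

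Three other places bear on how many enrolled caregivers will have week-2 data. Section 5.1 says that participants who withdraw or die are not replaced and still count towards accrual. Section 9.7 says that a survey not completed within two days of its time point is recorded as missing, for patients and caregivers alike. Section 10.1 (Missing Data) says that the analyses start with completers.

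**The concern.** Two power figures for the same visit stand in one paragraph and look comparable: 87% for patients and 90% for caregivers. The patient figure allows for missing data. The caregiver figure appears to treat the number enrolled as the number analysed. If so, they are on different footings, and the caregiver figure is somewhat optimistic.

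Caregiver outcomes are Specific Aim 2, and this is the only caregiver power statement in the document. A reader judging whether 180 caregivers are enough has nothing else to rely on.

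**Working it through.** **Inputs.** Difference 1.6 and SD 3.3 (Section 10.2), so d = 1.6/3.3 = 0.485. Two-sided alpha 0.05 (Section 10.2). Caregivers enrolled: 180 (Section 10.2). Patients are allocated 1:1 (Section 9.1: "Patients will be randomized in 1:1 fashion and stratified by study site and transplant type"), so I take 90 caregivers per arm. Caregivers follow their patient's allocation, so an exactly equal split is an assumption.

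**Formula.** With n evaluable per arm, the standardised difference is difference / (SD × √(2/n)). The normal approximation to power is Φ(standardised difference − 1.96). The two-sample t test, computed from the noncentral t distribution with 2n − 2 degrees of freedom, runs slightly lower.

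**Step 1: reproduce the caregiver figure.** At n = 90, 1.6 / (3.3 × √(2/90)) = 1.6/0.492 = 3.25, and Φ(3.25 − 1.96) = 90.2%. The t test gives 89.9%. Solving for 90% power by the normal approximation returns 90 per arm. The stated 90% therefore matches the full 180.

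**Step 2: check how the patient figure was built.** The inputs are 6.9 points and SD 20 (Section 10.2). With 10% missing, n = 180 × 0.9 = 162 per arm, and 6.9 / (20 × √(2/162)) = 6.9/2.222 = 3.105. Power is 87.4% (normal) or 87.2% (t test), matching the stated 87%. With no loss (180 per arm) it would be 90.5% (normal) or 90.4% (t test). So the 10% was deducted for patients, and nothing comparable was deducted for caregivers.

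**Step 3: caregiver power under a range of week-2 losses.** Evaluable n per arm is 90 × (1 − missing rate). At 10%, n = 81 and 1.6 / (3.3 × √(2/81)) = 1.6/0.519 = 3.086.

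| Missing at week 2 | Evaluable per arm | Normal approximation | t test |
|---|---|---|---|
| 0% | 90 | 90.2% | 89.9% |
| 2% | 88.2 | 89.6% | 89.3% |
| 5% | 85.5 | 88.7% | 88.3% |
| 10% | 81 | 87.0% | 86.6% |

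**Step 4: rule out sidedness.** A one-sided test would give 94.6% at 90 per arm and 92.5% at 81 per arm (normal approximation). Neither matches 90%.

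**Step 5: enrolment needed to keep 90% after a 10% loss.** 90/0.9 = 100 per arm, or 200 caregivers. That is 200/360 = 55.6% of patients, close to the 56% caregiver enrolment reported for the prior trial.

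**The case against.** The strongest reply is that the 90% follows correctly from the inputs written beside it. This stands: the issue is an unstated allowance, not an arithmetic slip.

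It can also be said that the 10% is not a caregiver assumption. That stands too. A reader might infer that the plan assumes 10% missing for caregivers and contradicts itself, but the 10% belongs to the sentence on patient QOL, and no caregiver rate appears anywhere. The week-2 rate quoted from the prior study is 2%, not identified as a caregiver rate, and at 2% the power is 89.3%. Against that, the sponsor chose not to plan on 2% for patients, and Section 11 expects missing data to be slightly higher in this multi-site trial.

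The enrolment figure may itself be cautious. The planned range is 180 to 360 (Sections 3.0, 4.0 and 9.1), and Section 19.2 expects at least 50%. At 56%, 0.56 × 360 is about 202 caregivers; after a 10% loss about 181 remain, and power is about 90%. Baseline adjustment, planned under Specific Aim 2 in Section 10.1, could also help: with a baseline correlation of 0.3 (an assumption; the documents give none), power at 81 per arm is about 90%. Both points limit the consequence, but Section 10.2 relies on neither. Its 90% is tied to 180 enrolled and reproduces without any adjustment.

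Two further inferences should be resisted. A reader might suppose that caregivers, who may be away from the hospital, will have less complete data than patients. The documents give no such comparison. Section 9.7 offers caregivers remote access, paper forms or telephone completion, with reminders, and the disease worsening and death listed in Section 11 fall most directly on patients. A reader might also apply the 15% rate to caregivers, but the plan uses it for 3 and 6 months, not week 2.

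**Conclusion.** The point holds and is minor. The stated 90% needs week-2 data from essentially all 180 enrolled caregivers, while the protocol's own rules let enrolled caregivers go without week-2 data and not be replaced. On the allowance used for patients at the same visit, power is about 87%, some 3 points lower. This rests on carrying over the patients' 10%, enrolment at exactly 180, an equal split and an unadjusted comparison. At 2% to 5% missing the shortfall is 1 to 2 points.

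It does not show that the caregiver comparison is underpowered. The endpoint is secondary, power stays above 80% at every loss considered, and no change to the sample size follows.

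**What to change.** In Section 10.2, state the missing-data allowance assumed for caregivers at week 2 and give the power that goes with it: about 87% with 180 enrolled and 10% missing. Alternatively, keep 90% and say that it needs about 180 evaluable caregivers, which means about 200 enrolled at 10% missing, within the planned 180 to 360.

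Either is a one-sentence edit. The first reports a slightly less favourable figure. The second sets a caregiver enrolment aim above the current floor. Neither alters the patient sample size or the analysis.

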10.3 Data security

Patient data will be collected at each institution (MGH, Duke, and Fred Hutchinson Cancer Research Center) using REDCap. Each site will maintain their own separate list of patient names and study IDs, which will be saved in password-protected files. Participants will be identified on study forms by case number only to protect confidentiality. Identifiers such as name will only be used during the initial data retrieval process and can be destroyed once all data records have been obtained and data analysis has been completed as discussed previously. At the completion of the study, de-identified data files will be transferred from Duke and Fred Hutchinson to the MGH using a secure data transfer.

Participants' responses to survey questions will remain confidential unless there is active suicidal ideation confirmed by the research team. Under these circumstances, as clearly stated in the patient consent form, the study RA will inform the site PI. The site PI will then determine the need to involve social work, psychiatry and/or take further action as deemed necessary.

In addition, as stated previously, all study staff at all participating sites will undergo an extensive training on study procedure and study procedures as well as data management to ensure data security and maintaining of confidentiality.

10.4 Quality control for collected data:

Our study staff will utilize double-data entry for approximately 10% of the data entered through REDCap to ensure high data quality. A research coordinator, blinded to the study intervention, will double enter 10% of the data through REDCap to check on data fidelity. If an error is found, the research coordinator will double enter an additional 5% of the data through REDCap. This process will continue until no errors are found.

11.0 Provisions to Monitor the Data to Ensure the Safety of Subjects*

Purpose of Multi-Center Data and Safety Monitoring Plan:

The purpose of the multi-center data and safety monitoring plan is to establish standards that will ensure that this Multi-Center protocol will comply with Federal Regulations, Health Insurance Portability and Accountability Act (HIPAA) requirements and applicable Dana Farber Harvard Cancer Center (DF/HCC) Standard Operating Procedures. Please see Appendix O for full details regarding Data and Safety Monitoring Plan.

General Roles and Responsibilities:

The overall PI ([name]) will work closely with [name] (co-investigator), who has expertise in conducting multi-site randomized palliative care trials, to ensure the successful implementation of the proposed multi-site project. [name] will be responsible for all aspects of conducting the multi-site protocol, which includes:

- Oversee the coordination, development, submission, and approval of the protocol as well as subsequent amendments.
- Ensure that the investigators, study team members, and participating institutions are qualified and appropriately resourced to conduct the protocol.
- Include a Multi-Center Data and Safety Monitoring Plan as detailed in this document and appendix O.
- Ensure all participating institutions are using the correct version of the protocol.

PROTOCOL TITLE: Multi-Site Randomized Trial of Inpatient Palliative Care for Patients with Hematologic Malignancies Undergoing Hematopoietic Stem Cell Transplantation

- Ensure that each participating investigator and study team member receives adequate protocol training and a site initiation visit prior to enrolling participants and throughout the trial's conduct as needed.
- Monitor progress and overall conduct of the study at all participating institutions.
- Review data and maintain timely submission of data for study analysis.
- Ensure compliance with all requirements as set forth in the Code of Federal Regulations, Dana Farber Harvard Cancer Center requirements, HIPAA requirements, and the approved protocol.
- Commit to provisions that the protocol will not be rewritten or modified by anyone other than the overall PI.
- Monitor accrual and address participating institutions that are not meeting their accrual requirements.

The Massachusetts General Hospital Cancer Center as the overall Coordinating Center will have the following responsibilities:

- Review registration materials for eligibility and register participants from participating institutions.
- Distribute protocol and informed consent document updates to participating institutions as needed.
- Oversee the data collection process from participating institutions.
- Maintain documentation of Serious Adverse Events (SAE) reports and deviations/violations submitted by participating institutions.
- Distribute SAEs that fall under the IRB Adverse Event Reporting Policy to all participating institutions.
- Maintain regulatory documents of all participating institutions which include but not limited to the following: local IRB approvals/notifications from all participating institutions, confirmation of Federal wise Assurances (FWAs) for all sites, all SAE submissions, screening logs for all sites, IRB approved consents for all sites.
- Conduct regular communications with all participating institution and maintain documentation of all relevant communications.

Each participating institution is expected to comply with all applicable federal regulations and requirements, the protocol and HIPAA requirements. Each participating institution will be responsible for the following:

- Document the delegation of research specific activities to study personnel.
- Commit to the accrual of participants to the protocol.
- Submit protocol and/or amendments to their local IRB.
- Maintain regulatory files.
- Provide the MGH Cancer Center with regulatory documents or source documents as requested.
- Participate in protocol training at the MGH Cancer Center during the initial study visit prior to enrolling participants.
- Participate in the two additional site visits to MGH throughout the study period.
- Update the MGH Cancer Center with research staff changes on a timely basis.
- Submit SAE reports to local IRB per local requirements and to the MGH Cancer Center, in accordance with the DF/HCC requirements.
- Submit protocol deviations and violations to the local IRB per local requirements and to the MGH Cancer Center in accordance with DF/HCC requirements.
- Have office space, office equipment, and internet access that meet HIPAA standards.
- Participate in quality assurance activities and meet with monitors or auditors at the conclusion of a visit to review findings.
- Promptly provide follow-up and/or corrective action plans for any monitoring queries or audit findings.

Intervention Training and Supervision:

PROTOCOL TITLE: Multi-Site Randomized Trial of Inpatient Palliative Care for Patients with Hematologic Malignancies Undergoing Hematopoietic Stem Cell Transplantation

- Intervention Training: We will use the inpatient palliative care intervention guide developed by Drs. [name], [name], and [name] in our previous single center randomized trial. As described in the study procedures section, Drs. [name] and [name] will provide initial training for all palliative care clinicians from all participating institutions using video conferencing to review the intervention guide (The site lead investigators will attend this training in-person). [name] will serve as the primary supervisor for the palliative care clinicians delivering the intervention.
- Assessment of Intervention Fidelity: To ensure the appropriate delivery of the palliative care intervention, Drs. [name], [name], and [name] will participate in monthly telephone conferences with the investigators and palliative care clinicians at participating sites to discuss any issues or concerns regarding the intervention. Moreover, palliative care clinicians will complete electronic surveys using Research Electronic Data Capture (REDCap) to report on the domains covered during their palliative care visits. Our research team has extensive experience using REDCap and utilized it in our prior study to collect information from palliative care clinicians about each clinical encounter. The brief REDCap Survey assesses domains and topics covered during the palliative care visit. We developed and refined the domains of inpatient palliative care and detailed the possible topics addressed under each domain based on our previous randomized trial. Drs. [name] and [name] will review the palliative care electronic surveys monthly for the first six months and then every 4 months thereafter to ensure adherence to the content of the intervention as specified by the intervention guide.

Informed Consent Requirements:

The Dana Farber Harvard Cancer Center approved informed consent document will serve as a template for the informed consent for participating institutions. The participating institution consent form must follow the consent template as closely as possible. Participating institutions are then to send their version of the informed consent document and HIPAA authorization, if a separate document, to the MGH Cancer Center for review and approval prior to submission to their local IRB. For all future consent versions, the approved consent form must also be submitted to the MGH Cancer Center after approval by the local IRB.

Multi-Center Protocol Confidentiality: All documents, investigative reports, or information relating to the participants are strictly confidential. Confidentiality is assured as participants will be identified on all study materials only by participant number, visit number, and date of visit. By recording the study data in this manner, the information can be considered 'de-identified,' and therefore compliant with the Standards for Privacy of Individually Identifiable Health Information ("Privacy Rule") of the Health Insurance Portability Act of 1996. Each participating site will keep participant data in computer file that is password protected and will change this password whenever the staff changes. Only the Principal Investigators and study staff will have access to the data. We will keep a link between participant number and participant's name in a separate file, also password-protected (with a different password).

Data Management Organizational Structure: Data forms will undergo a systematic and rigorous editing process prior to being keyed into the database. The research assistants at each participating site will routinely evaluate the data and discuss any problems and questions with the study staff, site-PIs, and the investigator team at the regular weekly team meetings. Data management formal reports on record status across the three following domains will be employed: entered, verified, and edited. These reports of data records will be evaluated once a month during the final team meeting of the month at each participating site. To help ensure data protection, backup copies, automatically generated by our computer systems, will be available.

Attrition Safeguards/Protection of Loss of Data:

A notable methodological consideration pertaining to the proposed research is protection against attrition. Our research group has conducted numerous clinical intervention studies. In our previous work, we have learned that individuals are best retained in studies when there is 1) a familiarity with study personnel (e.g., ability to

PROTOCOL TITLE: Multi-Site Randomized Trial of Inpatient Palliative Care for Patients with Hematologic Malignancies Undergoing Hematopoietic Stem Cell Transplantation

effectively establish rapport), 2) team-based persistence in conducting follow-up assessments, and 3) intervention sessions happening in tandem with ongoing medical appointments or inpatient hospitalizations. Yet, it is worth noting here a number of key issues that we have thoughtfully considered in the construction of the present proposal related to attrition. Attrition in clinical research studies overall occurs from three major sources: (a) disease worsening/mortality, (b) refusal to participate, and (c) loss of contact.

- **Disease Worsening/Mortality:** Given the burden of therapy for patients with hematologic malignancies undergoing HCT, we do anticipate that a minority of participants will be unable to complete the study protocol due to deteriorating health or death. Our research team has given considerable thought to this concern and adequately powered the study to account for missing data. In our prior single center randomized trial of the inpatient palliative care intervention, we only had 2% and 6.9% missing data at week-2 and 3-months post-HCT. We anticipate this percentage to be slightly higher in the proposed multi-site randomized trial given the multi-site study design and the inclusion of additional longitudinal assessments at six months and one year post-HCT. Nonetheless, the study research assistants will maintain detailed records for patient attrition due to disease-related factors at each participating site.
- **Refusal to Participate:** Participants who are successfully recruited into the study but later refuse to participate in subsequent intervention sessions pose a threat to the proposed study. In our previous trial, our refusal to participate rate after study enrollment was quite low at less than 1%. Again, the study research assistants will maintain detailed records for patient refusals at each participating site.
- **Loss of Contact:** Another source of attrition involves those subjects who are successfully recruited into the study but who cannot be located for subsequent follow-up assessments. Like attrition due to subject refusal, attrition due to loss of contact poses a threat to the proposed study. We do not anticipate this to be a major issue for the proposed study given the intensive and frequent outpatient follow-up visits for patients with hematologic malignancies during the first six months to one year post-HCT.
- **Participant Adherence:** To minimize attrition, we plan to use multiple strategies to reduce drop-out. Potential participants will be invited to participate in the baseline assessment during which time participants will receive a thorough explanation of the study treatments, requirements, and follow-up procedures. Study staff will emphasize the patient's responsibility as a research participant, reiterate confidentiality, and work to develop good rapport. Since the palliative care intervention occurs during the inpatient hospitalization for HCT, we do not anticipate any problems with adherence to the intervention visits. We will make a concerted and systematic effort to facilitate adherence to the completion of follow-up assessments. This task will be accomplished by: (1) obtaining longitudinal participant-reported measures during regular follow-up appointments; (2) providing participants with remote access to complete the longitudinal study measures; and (3) making reminder phone calls and administering the study measures over the phone if necessary for participants who do not have appointments in the window for assessment completion.

Data Safety and Monitoring Plan

The following procedures will be followed, in compliance with NIH requirements, to ensure the safety of study participants and the validity and integrity of data.

- **Range of Safety Reporting:** The research team (Drs. [name], [name], and [name]) will review all data pertaining to safety during their weekly meeting. The site PIs will also review all data pertaining to safety at their weekly site research meetings. These include adverse events (AEs) and SAEs, but also other data that may reflect differences in safety such as treatment retention rates and reasons for dropout. [name] will also lead a monthly meeting with all sites to discuss any issues pertaining to participant safety and data fidelity.
- **Data Repository:** The research team at the MGH Cancer Center has coordinated research initiatives over the past eight years that have established procedures and technologies for data collection and management. [name] will oversee all aspects of data collection for the study and the research assistants will have the operational responsibility of data management. Specifically, the research team will develop a study specific

PROTOCOL TITLE: Multi-Site Randomized Trial of Inpatient Palliative Care for Patients with Hematologic Malignancies Undergoing Hematopoietic Stem Cell Transplantation

data management protocol and standard operating procedures for the creation and testing of all study forms, data collection, quality control, and data extraction. These forms will be standardized. We will provide ongoing oversight of data management throughout the study, and will be responsible for generating reports and datasets for quality control and data analysis. All data management activities will utilize REDCap, a software toolset and workflow methodology for electronic collection and management of research and clinical trial data. REDCap data collection projects rely on a thorough study-specific data dictionary defined in an iterative self-documenting process by all members of the research team with planning assistance from Partners HealthCare Research Computing, Enterprise Research Infrastructure & Services (ERIS) group. REDCap provides secure, HIPAA compliant, web-based applications with an intuitive interface for users to enter data and have real time validation rules (with automated data type and range checks) at the time of entry.

